**5. LAY LANGUAGE SUMMARY OR SYNOPSIS (no more than one paragraph)**

Given the increasing recognition of the contribution of structural-level factors (e.g. gendered economic and social power imbalances) on both HIV and gender-based violence (GBV) among women, and thereby, the need for interventions that aim to alter such structures within communities, we have developed the proposed research to address the *intersection of GBV and HIV*. The proposed research aims to pilot a multi-strategy structural intervention combining community mobilization to promote gender equity alongside an economic intervention (microfinance and business training) in order to reduce gender-based violence and HIV risk among female sex workers (FSW) in Tijuana, Mexico. The program will be called ESTIMA: “Economic and Social empowerment To Increase upwards Mobility Among women”. The evaluation will employ a randomized controlled design, recruiting FSW (n=120, 60 in each arm) who will be randomized to: 1) ESTIMA (gender equity/community mobilization program and economic intervention) or 2) a wait-list control group. Women will be part of groups of approximately 6-10 women each, and each group will be randomized to intervention or control conditions. For this preliminary work, at 12 months follow-up, we hypothesize that compared to control participants, intervention participants will have: 1) significantly greater economic security (e.g. decreased debt, increased income, decreased number of sex trades) and 2) significantly greater perceived collective power (i.e. collective efficacy) to address gendered power imbalances within social structures and the community. The long-term goal of this program, upon future refinement and large scale implementation, is to reduce HIV risk behaviors, STI/HIV, GBV, and ultimately, alleviate a multitude of health burdens among women. Furthermore, we expect that such work will highlight the need for HIV prevention initiatives in Mexico, and elsewhere, to more broadly consider women’s ‘life contexts’ – addressing economic and social burdens in women’s lives, to reduce the burden of poverty, gender, and HIV, as well as the intersection of these among women.

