### **Phase II**

**2. To assess preliminary outcomes of the ESTIMA HIV Prevention Program** Using a two-armed randomized controlled design, we will recruit FSW (n=120, 60 in each arm) who will be randomized to: 1) the ESTIMA intervention (gender equity program and *Via* microfinance program) or 2) a wait-list control group. Women will be part of groups of approximately 10 women each, and each group will be randomized to intervention or control conditions. At 12 months follow-up, we hypothesize that compared to control participants, intervention participants will have: **a)** Significantly greater economic security (e.g. decreased debt, increased income, decreased number of sex trades) and **b)** Significantly greater perceived collective power (i.e. collective efficacy) to address gendered power imbalances within social structures and the community.

**3. To assess feasibility regarding all aspects of implementation, receptivity by participants and staff, and capacity to be maintained by *Via* microfinance efforts** Qualitative focus groups (n=2 or less per intervention group, 10 women per session), individual interviews (approximately 5 per intervention group), and quantitative assessments will be conducted with intervention participants, along with staff feedback via post-training evaluation forms, to inquire about satisfaction with and appropriateness of the program, as well as aspects pertinent to the ethical conduct of the intervention. We will also monitor recruitment, random assignment, adherence to intervention design, retention of participants, contamination across arms, and the incidence of adverse events.

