sexual health risk indicators). The distributional properties and reliability of continuously scaled variables will be examined. Effects of the intervention on both intermediate and long-term outcomes (see Figure 1) will be examined using logistic regression analyses for dichotomous variables (e.g. GBV, consistent condom use) and ANCOVA for continuous variables (e.g. collective efficacy scales, income, number of sex trades). Analyses will focus on outcomes at the 12 month follow-up. ANCOVA using ranks will be used to examine outcome variables with non-normal distributions, such as income. While ESTIMA is powered to focus on intermediate outcomes, we will also investigate trends on longer term outcomes as well (Figure 1). We expect low rates of loss to follow-up, as ESTIMA is incorporated into existing *Via* trainings; however, we will track any participants who drop out of the program (Aim 3), as well as loss to follow up. If there is more than a trivial amount of missing data, we will examine whether there are any patterns in missing data by relevant study variables (e.g. violence experiences, demographic characteristics etc). Power calculations were performed using a significance level of 0.05 and 80% retention (n=48 in each group), with focus on **primary intermediate outcome variables** (economic security and collective power variables) (Figure 1). For analysis focused on variables of income and debt, number of sex trades, as well as the scales measuring women's collective power, we will have 80% power to detect a standardized effect size of 0.5, which is considered a moderate effect size based on work from Cohen (1988). We believe that a moderate effect size would be needed in order to ensure that the effect of the intervention is significant for wide-scale adoption and sufficient impact. However, because we will have small numbers for this pilot of the ESTIMA project, we recognize that we may only be able to find trends to report, and which will be used to secure further funds to run a full-scale trial. While we have not powered the trial to detect a significant effect on GBV, HIV risk behaviors, or HIV/STI, we anticipate a trend toward decreased reports of these in the intervention group compared to the control arm. Furthermore, collecting information on GBV, HIV risk, and HIV/STI will also provide information to power a subsequent larger-scale evaluation.

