For Phase 2 (Aims 2-3), using a two-armed randomized controlled design, we will recruit FSW (n=120, 60 in each arm) from the parent study as well as via venue-based sampling methods similar to the parent study if needed (i.e. if we do not obtain sufficient numbers from the parent study to recruit) who will be randomized to: 1) the ESTIMA intervention (gender equity program and Via microfinance program) or 2) a wait-list control group. Women will be part of groups of approximately 10 women each, and each group will be randomized to intervention or control conditions. We will recruit ESTIMA participants from those who are completing 12 month follow-up for the parent study, using the same eligibility criteria and recruitment in Specific Aim 1 (assessing interest among those who indicate willingness to be recruited into this study), with an additional criteria related to women's drug use frequency; the specific criteria will be determined based on Aim 1 findings, consultation from the CAB and Via microfinance (drug use data will be retrieved from the parent survey; 41% and 53% report using drugs and alcohol less than once per week respectively). Those who participated in Aim 1 and who fall within these drug-related eligibility criteria are also eligible for participation. Research staff of ESTIMA and the parent grant will work jointly to identify those willing and eligible during the 12 months follow-up data collection of the parent grant, and explain the ESTIMA study to further assess interest. If we do not obtain at least 120 participants from the parent study we will conduct additional recruitment following the same recruitment protocol as the parent study (MAPA de Salud, PI: [name], protocol 100148).

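### The analysis and power calculation treat women as independent, although ESTIMA is delivered in groups and five places in the protocol randomise groups

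*Combined protocol and SAP*

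**What the plan says.** The only quantitative analysis text is the paragraph on data analyses and power in Section 9, under Specific Aim 2. Effects at 12 months are examined "using logistic regression analyses for dichotomous variables (e.g. GBV, consistent condom use) and ANCOVA for continuous variables". For skewed outcomes, "ANCOVA using ranks will be used to examine outcome variables with non-normal distributions, such as income". On sample size: "Power calculations were performed using a significance level of 0.05 and 80% retention (n=48 in each group", and from this the plan claims 80% power for a standardised effect of 0.5 on the economic security and collective power outcomes. Neither this paragraph nor any other part of the document mentions a group effect, ICC, design effect, GEE or robust variance.

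The unit of randomisation is described in two ways.

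- **Groups.** Section 5 says "each group will be randomized to intervention or control conditions". Section 6, Phase II says "Women will be part of groups of approximately 10 women each, and each group will be randomized to intervention or control conditions", and Section 10 says the same. Section 9 (Recruitment and Random Assignment) and Section 11 (Phase II) also have the microfinance groups formed and then randomised.
- **Women.** Section 5 also has "recruiting FSW (n=120, 60 in each arm) who will be randomized to: 1) ESTIMA", Section 6 has "we will recruit FSW (n=120, 60 in each arm) who will be randomized to: 1) the ESTIMA intervention", and Section 10 has women "who will be randomized to: 1) the ESTIMA intervention (gender equity program and Via microfinance program) or 2) a wait-list control group". A separate sentence in Section 9, the account of additional recruitment in Section 11, and Section 16 (about 20 women randomised to yield one ESTIMA group of 10) also read as individual allocation.

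Delivery is in groups on either reading. Section 9 describes lending to women as a group, collectives that elect leaders and set priorities, and training done entirely in groups. In Section 15, unpaid loans affect the group's later borrowing.

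**The concern.** Women in one ESTIMA group share trainers, a start date, a loan arrangement and a collective. The primary outcomes, economic security and collective efficacy, are what those shared processes are meant to change. Outcomes within a group are therefore likely to be positively correlated. If so, 48 women carry less information than 48 independent women, and the planned tests do not allow for it. Entering group as an ordinary covariate would not help, because each group lies wholly within one arm.

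Sections 5 and 6 hypothesise significant differences, and Section 9 intends to use the results to seek a full-scale trial. Overstated precision would carry into that trial's planning. If group membership is not recorded, no ICC could be estimated for it either.

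**Working it through.** **Inputs from the documents.** 60 women per arm and 80% retention, so 60 x 0.8 = 48 analysed per arm; significance level 0.05, sidedness not stated; effect 0.5 SD; groups of about 6-10. That gives 60/10 = 6 groups per arm with 8 women retained in each, or 60/6 = 10 groups with 4.8 retained on average.

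**Assumed.** ICC of the baseline-adjusted outcome from 0.01 to 0.20; baseline-outcome correlation r = 0.5 unless stated.

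**1. Reproducing the 80%.** For independent women, SE = sqrt(2/48) = 0.204 and 0.5/0.204 = 2.449.
- One-sided, no covariate: Phi(2.449 - 1.645) = 0.79 (0.78 from the t distribution).
- Two-sided, no covariate: Phi(2.449 - 1.960) = 0.69 (0.68 from t).
- Two-sided with r = 0.5: residual SD = sqrt(1 - 0.25) = 0.866, 2.449/0.866 = 2.828, Phi(2.828 - 1.960) = 0.81 (0.80 from t).

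The stated figure is reached one-sided, or two-sided with an unstated baseline correlation near 0.5. Neither leaves room for a design effect.

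**2. Size of the distortion, by formula.** DE = 1 + (m - 1) x ICC. At ICC 0.05:
- m = 8: DE = 1 + 7 x 0.05 = 1.35; effective n = 48/1.35 = 35.6; true-to-naive SE ratio = sqrt(1.35) = 1.16.
- m = 4.8: DE = 1 + 3.8 x 0.05 = 1.19; effective n = 48/1.19 = 40.3; ratio 1.09.

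True two-sided level of the naive test = 2[1 - Phi(1.96/sqrt(DE))]. With both arms clustered this is 9.2% (m = 8) or 7.2% (m = 4.8). With only the ESTIMA arm clustered, the variance factor is the average of DE and 1, that is 1.175 or 1.095, giving 7.1% or 6.1%.

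**3. Simulated false-positive rates of the planned tests.** The ranges cover ANCOVA and rank ANCOVA (100,000 null runs per cell), logistic regression without a covariate at prevalence 0.3 and 0.5 (40,000 runs), and both group layouts.

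| ICC | ESTIMA arm only | Both arms equally |
|---|---|---|
| 0.01 | 4.9-5.7% | 5.4-6.0% |
| 0.02 | 5.1-6.0% | 5.6-7.1% |
| 0.05 | 5.9-7.3% | 6.9-9.7% |
| 0.10 | 7.0-9.5% | 9.2-13.8% |
| 0.20 | 9.2-13.8% | 13.6-21.6% |

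There is one exception. ANCOVA on an unranked log-normal outcome, for which the plan uses ranks instead, gives 4.4-4.8% at ICC 0.01-0.02 and 5.2-5.7% at 0.05, with the ESTIMA arm only clustered.

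**4. Do corrected tests hold their level?** A t test on baseline-adjusted group means, with df = number of groups minus 2, gave 4.5-5.4% on values and ranks and 4.8-6.2% on proportions. A partially nested analysis (group effect in the ESTIMA arm only) gave 4.7-5.3% on continuous and 4.9-6.4% on binary outcomes when only that arm clustered. When control groups also correlated (ICC 0.05-0.20) it gave 5.4-10.0%, so it is unsuitable if groups are randomised.

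**5. Power, two-sided, effect 0.5, r = 0.5.**

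| Test | ICC 0 | 0.05 | 0.10 | 0.20 |
|---|---|---|---|---|
| Partially nested, ESTIMA arm clustered | 75-78% | 68-74% | 61-70% | 50-63% |
| Group-mean t, both arms clustered | 71-76% | 60-68% | 50-62% | 38-52% |

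The planned ANCOVA still rejects 78-79% of the time at ICC 0.05 with ESTIMA-arm clustering. Its main fault is false positives, not lost power. The baseline correlation matters: at ICC 0.05, r = 0 gives 56-61% (partially nested) and 48-56% (group-mean), while r = 0.7 gives 83-88% and 76-84%.

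**The case against.** The strongest case against is that the harm depends on an ICC nobody knows. At 0.02 or below the excess is minor, and the both-arms column is an upper range. Before 12 months, wait-list women receive only referrals and testing, so the programme does nothing to link them, and the most operational account of allocation (Section 16) is individual. Economic outcomes may also cluster less than collective efficacy, because each woman has her own loan amount and her own duty to repay. Finally, this is a pilot, and Section 9 concedes that it may yield only trends.

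Much of this bears on size, and it stands to that extent. Under individual randomisation the ESTIMA-arm column is the relevant one, and one ICC need not fit every outcome. None of it supplies the missing allowance. If groups are randomised, control groups are units of allocation whether or not they meet. The caveat about trends concerns small numbers, not correlated ones, and sits beside a claim of 80% power. It is also fair to say that the group-mean t test is not the only valid choice: a mixed model with small-sample degrees of freedom would serve as well.

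**Conclusion.** The concern holds. Followed as written, the plan understates standard errors whenever positive within-group correlation remains after baseline adjustment, and this affects every planned between-arm test as well as the power statement. That group structure is left out is certain from the text. The direction of the error follows from positive correlation, apart from the unranked log-normal case at very low ICC. The size rests on an assumed ICC: at 0.05 to 0.10 the nominal 5% level becomes roughly 6-10% with clustering in the ESTIMA arm only and 7-14% with clustering in both. It should be corrected before analysis. The group record should start as groups form, because membership may be hard to reconstruct later.

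**What to change.** 1. Reconcile the unit of randomisation across Sections 5, 6, 9, 10, 11 and 16. Record a group identifier as groups form: for every woman if groups are randomised, and for every ESTIMA woman if women are. Individually randomised controls have no group and are analysed as individuals.
2. If groups are randomised, make the primary analysis a t test on baseline-adjusted group means: of values, of ranks for income and other skewed outcomes, and of proportions for binary outcomes. Adjust for baseline with one slope pooled over individual women; groups minus 2 degrees of freedom then held the error at 4.6-5.5% in a separate simulation. An equivalent mixed model with a small-sample correction is acceptable.
3. If women are randomised, use a partially nested model with a group effect in the ESTIMA arm only, the baseline value as covariate and Satterthwaite degrees of freedom. State the version for binary outcomes explicitly. Do not use this model if groups are randomised.
4. Restate power for the chosen test, giving sidedness, the assumed baseline correlation and a range of ICCs.

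The cost is a group identifier and new analysis text, with no added participants or visits. Intervals will be wider and stated power lower. Some of that loss remains even at ICC 0, because the degrees of freedom are fewer.

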## **Phase II**

### **Specific Aim 2: To assess preliminary outcomes of ESTIMA**

**Recruitment and Random Assignment.** We will recruit ESTIMA participants from those who are completing 12 month follow-up for the parent study, using the same eligibility criteria and recruitment in Specific Aim 1 (assessing interest among those who indicate willingness to be recruited into a sub-study and based on responses in their surveys from the parent study), with an additional criteria related to women's drug use frequency; the specific criteria will be determined based on Aim 1 findings, consultation from the CAB and *Via* microfinance (drug use data will be retrieved from the parent survey; 41% and 53% of participants from the parent study report using drugs and alcohol less than once per week respectively). *Those who participated in Aim 1 and who fall within these eligibility criteria will be eligible for participation.* Research staff of the K01 and parent grant will work jointly to identify those willing and eligible during the 12 months follow-up data collection of the parent grant. From the parent study, we will recruit a total of 120 participants in expectation to afford a final sample size of at least 48 in each group (using a conservative estimate of 80% retention). Eligible and willing participants will be randomized to treatment assignment (ESTIMA or wait-list control group) using a randomizer software package, after enrollment. The microfinance groups of women (approximately 6-10 per group) will be formed and randomized to intervention or wait-list control condition. The wait-list control group will be provided with referrals to local FSW support organizations, as the standard of care (STI/HIV testing and referrals), and will receive ESTIMA subsequent to the 12 month follow-up data collection. ESTIMA will involve groups of approximately 6-10 women each; groups will initiate once sufficient numbers are enrolled (i.e. groups will be staggered in terms in initiation).

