Survey/Specimen Data Collection. The survey is expected to take approximately 45 minutes and approximately 30 minutes for STI/HIV testing; overall, with waiting times, we expect this aspect of study participation to take approximately 90 minutes. For the baseline ESTIMA survey and HIV/STI testing, we will use data collected from the parent study's 18 months follow-up survey and specimen collection. Participants recruited outside of the parent study will be provided with the survey and STI testing, and reimbursed for their time in the amount of \$30 (at baseline and 12 month follow-up) and \$20 at 6 month follow-up (survey but no STI testing). All participants will also complete a 5-10-minute supplemental survey during informed consent or at another time preferred by the participant and will measure greater details on women's alcohol use frequency and experiences of discrimination; these measures were not asked in the parent study survey but will be important to examine in terms of assessing intervention impact. For the ESTIMA 6 month follow-up, we will use survey data collected from the same survey as implemented at baseline (including the additional questions on alcohol use frequency and experiences of discrimination). Final 12 month follow-up for ESTIMA will be conducted independently of the parent study.. (We have budgeted for the costs associated with testing of ESTIMA participants for the 6 and 12 month follow-up, whereas the baseline will be conducted under the parent study. Trained research assistants arrange a follow-up interview time to be conducted at the study office via contact information collected as part of the parent grant. After providing informed consent, participants complete a 60 minute interviewer-administered survey using computer assisted personal interviewing (CAPI) (NOVA software, MD, USA). The survey (and any new items for the ESTIMA project) will be translated into Spanish, back-translated to English and reviewed for accuracy by the bilingual project coordinator and project consultants, who have also reviewed questions for cultural and linguistic appropriateness. Women will be reimbursed \$30 for the survey and testing (at baseline and 12 month follow-up) and \$20 at 6 month follow-up (survey but no STI testing). Data collection interviewers will not be aware of women's treatment assignment. Women who test positive for any HIV/STI test will be provided with appropriate treatment and/or referral to HIV care services. A participant tracking system will be developed during enrollment for the ESTIMA project in order to collect follow-up data (which will take place at the same study office) and kept up to date with information on address, phone number, etc., and all contact attempts. Permission to use different tracking methods (e.g. contacting friends) will be obtained at enrollment and kept current in order for us to collect the additional assessment after participants' involvement in the parent study ends (our 12 month follow-up). A key study aim is to identify retention challenges, which will be monitored quantitatively and qualitatively (Aim 3). Given that we are recruiting from the 18 month follow-up of the parent study, we also expect to recruit women who have a low probability of attrition, given that they were already among those not lost to follow-up for the 18 month data collection of the parent study. While we will use the parent study's 18 month follow-up data, we do not expect to see reductions in our outcome measures of interest until 12 months follow-up. However, 6 month follow-up may be useful to conduct mediational analyses to understand patterns in or variations of change in the outcome variables.

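### Missing 12-month outcomes get only a pattern check, and the 6-month outcomes already collected stay out of the effect estimate; loss linked to outcomes differently by arm can then bias the result

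*Combined protocol and SAP*

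**What the plan says.** All references are to the combined protocol and SAP.

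- **Design.** Section 6, Phase II: "we will recruit FSW (n=120, 60 in each arm").
- **Analysis.** Section 9, Quantitative Data Analyses and Power Calculations, names logistic regression for dichotomous outcomes, ANCOVA for continuous ones and ANCOVA on ranks for non-normal ones such as income. It adds: "Analyses will focus on outcomes at the 12 month follow-up".
- **Sizing.** The same section: "Power calculations were performed using a significance level of 0.05 and 80% retention (n=48 in each group"), and "we will have 80% power to detect a standardized effect size of 0.5". Under Recruitment and Random Assignment the sample is set "using a conservative estimate of 80% retention".
- **Expected loss.** "We expect low rates of loss to follow-up, as ESTIMA is incorporated into existing" Via trainings. No rate is given, overall or by arm.
- **Missing data.** If the amount is more than trivial (not defined), "we will examine whether there are any patterns in missing data" by study variables. There is no analysis set, imputation, likelihood-based repeated-measures model, weighting or sensitivity analysis.
- **6-month data.** Survey/Specimen Data Collection repeats the baseline survey at 6 months. The only use given is that "6 month follow-up may be useful to conduct mediational analyses".

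**The concern.** Looking for patterns in missing data describes a problem without changing the estimate. With single-visit models and 48 per arm, the default is to compare the women who have a 12-month value.

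Loss related to outcomes differently by arm is plausible here. The reason given for low loss, that ESTIMA sits inside existing trainings, can apply only to the ESTIMA arm. Wait-list women receive the programme after the 12-month data collection. Before then, only ESTIMA women take a loan through the study, due within 4 months (Section 9). Sections 14 and 15 accept that some may have trouble repaying. Debt is among the primary intermediate outcomes. It is an inference, though a reasonable one, that women in repayment difficulty would be harder to retain and that the difficulty would show in the 6-month survey.

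At stake is the effect estimate that the plan intends to use in seeking funds for a full-scale trial.

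**Working it through.** **1. The plan's own figures.** 60 × 0.80 = 48 per arm, which reproduces exactly. For power at 0.5 SD with 48 per arm (normal approximation):

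- two-sided, unadjusted: 0.5 × √(48/2) − 1.960 = 2.449 − 1.960 = 0.489, giving 68.8%;
- one-sided: 2.449 − 1.645 = 0.804, giving 78.9%;
- two-sided ANCOVA with baseline correlation 0.5: (0.5/√0.75) × √24 − 1.960 = 2.828 − 1.960 = 0.868, giving 80.7%.

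The stated 80% therefore fits the last two variants, neither of which is spelled out. The ANCOVA variant is used below.

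**2. Size of bias in principle.** If a fraction *f* of one arm is lost, and the lost women differ from retained women by *d* SD after baseline adjustment, the bias is *f* × *d*. With *f* = 0.20: 0.20 × 0.25 = 0.05 SD, and 0.20 × 0.50 = 0.10 SD.

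**3. Large-sample check.** The documents give no correlations and no loss by arm, so all of these are assumptions: 1,000,000 women per arm, outcome SD 1, all correlations 0.5, and dropout logit slope 1 per SD where loss is informative. The true 12-month effect is 0.5 (0 in rows marked \*). Lost women have a 6-month value unless stated.

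| Loss, ESTIMA / control | What drives loss | Completers' ANCOVA bias (SD) | Bias using 6-month data, MAR (SD) |
|---|---|---|---|
| 30% / 10% \* | arm only | −0.002 | −0.002 |
| 30% / 10% | baseline value | −0.001 | −0.001 |
| 20% / 20% | 6-month value, same in both arms | 0.000 | 0.000 |
| 20% / 20% | 6-month value in ESTIMA; random in control | +0.044 | +0.001 |
| 20% / 20% | low 6-month values leave ESTIMA, high ones leave control | +0.089 | 0.000 |
| 30% / 10% | 6-month value, same slope in both arms | +0.041 | 0.000 |
| 30% / 10% | 6-month value in ESTIMA; random in control | +0.065 | 0.000 |
| 30% / 10% \* | as above, half of those lost also missed 6 months | +0.066 | +0.028 |
| 30% / 10% \* | unseen 12-month value in ESTIMA; random in control | +0.192 | +0.176 |

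**4. Trial-sized check.** 60 per arm, 3,000 trials per scenario, true effect 0.50. ESTIMA loss was 20% at random, and control dropout logit was −1.6 − slope × 6-month value (control loss about 21% to 24%). Baseline correlated 0.5 with each follow-up. Two separate runs agreed to within 0.01.

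| 6-to-12-month correlation | Slope | Completers' estimate | Bias |
|---|---|---|---|
| 0.5 | 1.0 | 0.45 | −0.05 |
| 0.5 | 1.5 | 0.43 to 0.44 | −0.06 to −0.07 |
| 0.7 | 1.0 | 0.42 | −0.08 |
| 0.7 | 1.5 | 0.38 | −0.12 |

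Using baseline and 6-month values by arm gave 0.49 to 0.51 throughout. The sign is opposite to step 3 because here poorly doing control women leave.

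**5. Against sampling error.** With 42 and 54 analysed (60 × 0.70 and 60 × 0.90) and baseline correlation 0.5, SE = √[0.75 × (1/42 + 1/54)] = 0.178 SD. The bias is 0.04/0.18 = 0.22 to 0.12/0.18 = 0.67 of one SE, and 8% to 24% of the 0.5 target. Clustering by randomised group is ignored; allowing for it would enlarge the SE.

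**6. The within-woman term is essential.** In the step 4 scenarios (500,000 per arm), a two-visit model with independent residuals gave 0.457, 0.435, 0.420 and 0.376. Completers' ANCOVA gave 0.457, 0.434, 0.420 and 0.374. Without that term, adding the 6-month visit corrects nothing.

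**The case against.** The strongest reply is that the plan works to prevent loss in both arms. It has a tracking system, paid surveys at 6 and 12 months, small payments for updating contact details, travel help for women who move, and many women already retained through the parent study (Sections 9, 11 and 20). Waiting for ESTIMA may itself keep control women in the study. Retention is an Aim 3 outcome, and missing-data reports run at least every two weeks. The plan describes a small pilot that may show only trends, and the bias found is smaller than the standard error.

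Much of this stands, and it rules out several stronger readings that a reader might infer:

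- *That the plan expects 20% loss.* It does not. The figure is a conservative sizing allowance, and low loss is expected.
- *That the plan prescribes a completers' analysis.* This is implied by the named models and the 48 per arm, but not stated.
- *That unequal loss by itself biases the comparison.* The bias was zero to rounding at 30%/10% when loss depended only on arm or baseline.
- *That informative loss differing by arm is the expected case.* The documents give no loss by arm, so it is plausible and no more.

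What the reply does not supply is a method for the outcomes that are still missing. Retention through the parent study also says nothing about women recruited outside it. The plan's view that outcomes will not move before 12 months is no bar to using the 6-month values: they help because they predict the 12-month value and dropout, whether or not an effect has appeared by then.

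**Conclusion.** The point holds in a limited form. The plan has no method for missing 12-month outcomes beyond a pattern check, and it leaves relevant data that it already collects out of the estimate. If loss is related to post-baseline outcomes so that the retained women shift by different amounts in the two arms, the completers' estimate can be biased. Under the assumptions shown the bias is about 0.04 to 0.12 SD, in either direction, against a target of 0.5 SD and a standard error of about 0.18 SD. The upper end needs the steeper dropout slope and a 6-to-12-month correlation of 0.7 together.

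It would also be too strong to say that the 6-month data solve the problem. They remove the bias only if loss is explained by observed values. The correction is partial if women lost at 12 months also missed 6 months (0.028 of 0.066 SD remained), and it barely helps if loss depends on the unseen 12-month outcome (0.18 against 0.19 SD). The checks used normally distributed outcomes; no size was established for rank or binary outcomes. This is a cheap improvement, not a flaw that invalidates the trial.

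**What to change.** State in the Quantitative Data Analyses section:

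1. **Analysis set:** all randomised women, in their assigned arm.
2. **Continuous outcomes:** a repeated-measures model of the 6- and 12-month values with arm, visit, arm-by-visit, baseline and baseline-by-visit. Include an unstructured within-woman covariance or a participant random effect, and a random effect for the randomised group. The 12-month contrast is the estimate.
3. **Rank and binary outcomes:** multiple imputation by arm including baseline and 6-month values, with an analysis that respects the randomised groups. This covers survey outcomes. HIV/STI results have no 6-month value where that visit is survey only, as Section 20 states.
4. **Reporting:** loss by arm and visit, including women with no follow-up value, who contribute no outcome to the model in item 2.
5. **Sensitivity:** keep the completers' ANCOVA, and add a delta-shift analysis in which missing 12-month values are made worse or better by stated amounts in one arm.

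The cost is SAP wording and slightly more analysis work, with no new data. The main estimate would then rely on data being missing at random, which item 5 is there to test.
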